**EFFECT OF INTRAVENOUS LIGNOCAINE INFUSION ON INTRAOPERATIVE
END TIDAL DESFLURANE CONCENTRATION REQUIREMENTS: A
RANDOMISED DOUBLE-BLINDED CONTROLLED STUDY**

Document Date: 25/05/2021

INTRODUCTION

Lignocaine is an amide local anaesthetic and class 1B antiarrhythmic that is widely used in all medical and surgical fields. It also contains analgesic, antinociceptive, immunomodulating and anti-inflammatory actions.¹ There are many clinical studies demonstrating lignocaine's many perioperative benefits. Yang et al (2020) in a systemic and meta-analysis review showed that giving IV lignocaine in the perioperative period was safe, reduced airway complications, obtunds cough reflex and reduce sore throat.² Other reported advantages of systemic lignocaine administration include pain reduction, reduced opioid consumption, nausea, ileus duration and length of hospital stay.³⁻⁶ These benefits has been shown to persist from the onset of its effects up to 36 hours after infusion has been terminated.^{5,7}

In addition to its analgesic properties, systemic lignocaine has a minimum alveolar concentration (MAC) sparring effect on volatile anaesthetics which has been proved in multiple animal studies.⁸⁻¹¹ The mechanism for lignocaine's MAC sparring effect is likely due to blockage of sodium channels.⁸ Recently, Omar et al (2019) and Weinberg et al (2017) demonstrated in their clinical studies that parenteral lignocaine reduced Bispectral index (BIS) guided sevoflurane requirements.^{12,13} Weinberg et al (2017) also tabulated data from numerous trials which detailed the effects of parenteral lignocaine in reducing volatile agent requirements.¹³ Cardiovascular depression and risk of post-operative nausea and vomiting are related to volatile agents in a dose dependent manner.^{14,15} Lower volatile agents requirement should result in a more favourable cardiovascular profile which would be beneficial in hypovolemic patients and those with low cardiac reserves. Furthermore, coupled with opioid reduction, incidence of post-operative nausea and vomiting could be reduced. Awakening from volatile agent anaesthesia is dependent on its washout from alveolar ventilation and its dose at end of surgery.¹⁶ Therefore, it is postulated that emergence and extubation time might be faster resulting in more efficient utilisation of the operation theatre.

Clinical effects of IV lignocaine infusion are widely reported to be seen at 1-2 mg kg⁻¹ h⁻¹ which results in plasma levels below 5 mcg ml⁻¹.^{3-5,7,17} Context sensitive halftime after a 3-day infusion is about 20-40 min and there is no accumulation in healthy individuals.⁵ However, its clinical effectiveness differs between types of surgery, possibly due to sample size and design of the studies.³ Patient safety is of paramount importance hence it should be noted that measurement of plasma levels of lignocaine is not widely available in Malaysia and

there is limited data regarding its optimal dosing and duration. Lignocaine has a narrow therapeutic index whereby CNS toxicity (numbness of tongue, metallic taste, light headedness and tinnitus) will begin to manifest when plasma concentration exceeds 5 mcg ml⁻¹ and if left untreated, will progress to visual disturbances, muscle twitching, unconsciousness, seizure, respiratory arrest and cardiovascular collapse.⁵ Cardiovascular toxicity is a rare and late complication as it usually occurs at plasma levels exceeding 10 mcg ml⁻¹ which is well above that is required for neurological toxicity.⁵ In the event of severe toxicity, intralipid can be given as per the guideline provided by the Association of Anaesthetists for Great Britain and Ireland.

Desflurane is an inhalational anaesthetic agent with a low blood: gas coefficient (0.42) which allows for more precise control of the level of anaesthesia, rapid induction and rapid emergence resulting in shorter recovery when compared to other inhalational agents like sevoflurane.^{18, 14, 19} Therefore, it is preferably used for long surgery, bariatric surgery, obese patients or elderly patients as the faster offset leads to early wake up which minimises the risk of respiratory depression that is commonly associated with these cases.^{14, 18, 19} These characteristics also makes it suitable for ambulatory and day-care surgery.¹⁴ As little as 0.02% are metabolised in vivo, hence no dose adjustment is needed for patients with renal or hepatic dysfunction while the rest are vented to the environment without much or any degradation.^{14, 18, 19} However, due to its high cost, it is not widely used for all cases.

To the best of our knowledge, there is no research on the effects of IV lignocaine infusion on intraoperative desflurane requirements in human population. Reduction of desflurane requirements when coupled with the reported benefits of IV lignocaine, will contribute to a high quality, cost effective, optimal, balanced and safe provision of anaesthesia.

OBJECTIVE

1. To investigate the effect of IV lignocaine on the end tidal desflurane concentration required to maintain BIS values between 40-60.
2. To compare intraoperative haemodynamic changes in patient with intravenous lignocaine vs normal saline.

MATERIALS AND METHODS

This prospective, double-blinded, randomised controlled study will be submitted for the approval of the Research Committee of Department of Anaesthesiology & Intensive Care, Universiti Kebangsaan Malaysia Medical Centre (UKMMC), Research & Ethics Committee, UKMMC and will be registered at ClinicalTrials.gov.

Written informed consent will be obtained from selected patients recruited into the study, which will be conducted by a single operator who is the principal investigator of this study. The study will be conducted in Hospital Universiti Kebangsaan Malaysia, Kuala Lumpur.

Inclusion Criteria:

1. American Society of Anaesthesiology (ASA) I or II patients.
2. Patients aged between 18-75 years of age.
3. Patients scheduled for elective laparoscopic cholecystectomy.
4. Patients scheduled for laparoscopic hernioplasty.
5. Patients scheduled for emergency laparoscopic appendicectomy.
6. Patients scheduled for emergency laparoscopic cystectomy.
7. Patient weight ranging from 50 – 100 kg.
8. Surgery lasting at least one hour.

Exclusion Criteria:

1. Patients with a known allergy to study drug.
2. Patients with body mass index (BMI) more than 35 kg m⁻².
3. Patients who are taking sedatives.

4. Patients with chronic substance abuse.
5. Patients with history of seizures, psychiatric disorders, cardiac failure, arrhythmias, hepatic or renal dysfunction.
6. Patients who are taking class IB antiarrhythmics or amiodarone.
7. Surgery lasting more than 3 hours.

Methodology:

Patient will be reviewed and recruited during premedication round, written consent will be explained and obtained. Patients will be fasted for at least six hours before their surgery. Tablet paracetamol 1g will be given to patients once they are called to operation theatre.

Patients will be randomly assigned into two groups based on computer generated randomisation tables. Group A will receive intraoperative lignocaine while Group B will receive normal saline. The study drugs will be prepared by an anaesthetist registrar who is not involved in the study. Each drug syringe will be coded and given to the primary investigator who will be blinded.

In the operation theatre, intravenous access will be obtained using an 18 G cannula in all patients and infusion of crystalloid will be started. Standard monitoring will then be applied using continuous electrocardiography (ECG), non-invasive blood pressure (NIBP) monitoring, pulse oximetry and capnography. BIS (BIS Quatro™, USA) will be used to assess the depth of anaesthesia for all patients and baseline values for BIS shall be obtained prior to induction. Pre induction blood pressure (BP) and heart rate (HR) will also be recorded. The study drugs will be given 5 min before induction of anaesthesia and two syringe pumps will be used to deliver the study drugs. First, a bolus of the study drug prepared in a 10 ml syringe will be given to the patient over a period of 3 min via the syringe pump. The time of initiation of the bolus will be taken. After bolus, the BP and HR will be recorded. Subsequently, infusion of the study drug prepared in a 20 ml syringe will be started and continued until the end of surgery using the other syringe pump. The time at the start of infusion will be taken.

Group A will receive an IV bolus dose of 1.5 mg kg^{-1} of 2% lignocaine HCL diluted up to 10 ml with normal saline in a 10 ml syringe which will be delivered via a syringe pump over a period of 3 min. This is then followed by an IV infusion at the rate of $1 \text{ mg kg}^{-1} \text{ h}^{-1}$ of 2%

lignocaine HCL in a 20 ml syringe which will be administered by another syringe pump. Patients in Group B will receive an IV bolus of 10 ml of normal saline over a period of 3 min followed by an IV infusion of an equal volume of normal saline, both of which will be delivered by separate syringe pumps.

Anaesthesia will be induced with IV fentanyl 2 mcg kg⁻¹ followed by IV propofol 2-3 mg kg⁻¹ and IV rocuronium 0.6 mg kg⁻¹. After 3 minutes of mask ventilation with only 100% oxygen, tracheal intubation using an appropriately sized endotracheal tube (ETT) will be performed to secure patient's airway. The patient will then be connected to Aisys CS² anaesthesia machine and the lungs will be ventilated with desflurane in 50% oxygen-air balance at a tidal volume of 6-8 ml kg⁻¹. End tidal CO₂ (EtCO₂) level will be maintained between 35-45 by adjusting the respiratory rate. The time of induction and intubation will be documented.

Anaesthesia shall be maintained with desflurane, in 50% oxygen-air balance with a total flow of 1.0 L min⁻¹. The end tidal desflurane (Et-Des) concentration will be adjusted to maintain a target BIS of between 40-60. BIS, MAC values, Et-Des concentration, BP and HR will be recorded every 10 min from the time of induction until the end of surgery. IV parecoxib 40 mg will be given to all patients. Boluses of IV fentanyl 50 mcg will also be given to maintain blood pressures within 20% of pre-operative levels. Dosage of fentanyl given post induction will be recorded. Bolus of IV ephedrine 6 mg will be given during hypotensive episodes with HR less than 60 beat per min while those with normal HR will be given a bolus of IV phenylephrine 100 mcg. Patients will also be given IV dexamethasone 8 mg post induction and IV granisetron 1 mg 30 mins before end of surgery to reduce the risk of post-operative nausea and vomiting. Core temperatures will be maintained above 35 °C with fluid warmer and warming blanket. If surgery lasts more than 3 hours, patient will be excluded from the study and infusion of the study drug will be stopped.

Desflurane and study infusions will be discontinued and estimation of desflurane cost will be estimated at the end of surgery. Neuromuscular block will be reversed with a combination of IV atropine 1 mg and IV neostigmine 2.5 mg. When the patient meets all criteria for extubation, the ETT will be removed. Time to extubation (defined as time from desflurane discontinuation to tracheal extubation) will be recorded. Pain score will be assessed in recovery bay and if required, patient will be given patient-controlled analgesia morphine.

Signs of lignocaine toxicity will be monitored in all patients beginning from the time of bolus of the study drug until one-hour post operatively in the recovery bay. During general anaesthesia, signs of lignocaine toxicity that will be looked out for include an initial tachycardia and hypertension followed by prolonged PR interval, widened QRS, sinus bradycardia, ventricular arrhythmias, hypotension and cardiac arrest. When the patient is awake in recovery bay, along with late signs of lignocaine toxicity as mentioned above, patient will be observed for one hour for early signs and symptoms characterised by perioral numbness, tinnitus, light headedness, visual disturbances, muscle twitching, seizure, altered mental state and respiratory arrest. If any of these were to occur, then infusion of the study drug will be stopped and these patients will be excluded from the study and managed according to hospital protocol.

STATISCAL ANALYSIS

a) Sample size calculation:

The α value is set at 0.01 and power of study at 90%. The sample size is calculated using t- test. Calculation as derived from a study by Kuo et al (2006) and Omar et al (2019).^{6, 12}

The sample size is calculated using the “Power and Sample Size Calculations” program.

Sample size was calculated using t-test.

Requested output: Sample size

Design: Independent

Input: $\alpha = 0.01$; power = 0.9; $\delta = 0.5$; $\sigma = 0.4$; $M = 1$

[figure not shown]
Case sample size: 21 x 2 plus 10% drop out rate = 48

Sample = 24 per study group

b) Statistical test:

Analysis will be analysed using SPSS software for windows. The Kolmogorov-Smirnov test will be used to assess variable normality distribution. Categorical variables will be analysed by chi square test. Continuous variables will be compared using student's t -test. p value less than 0.05 will be regarded as statistically significant.

FLOW CHART

AAGBI Safety Guidelines

Management of Severe Local Anaesthetic Toxicity

1 Recognition	Signs of severe toxicity: 
 Sudden alteration in mental state, severe agitation or loss of consciousness, with or without tonic-clonic convulsions Cardiovascular collapse: sinus bradycardia, conduction blocks, asystole and ventricular tachyarrhythmias may occur Local anaesthetic (LA) toxicity may occur some time after an initial injection 	
2 Immediate management	
 Stop injecting the LA Call for help Maintain the airway and, if necessary, secure it with a tracheal tube Give 100% oxygen and ensure adequate lung ventilation (hyperventilation may help by increasing plasma pH in the presence of metabolic acidosis) Confirm or establish intravenous access Control seizures: give a benzodiazepine, thiopental or propofol in small incremental doses Consider drawing blood for analysis, but do not delay definitive treatment to do this 	
3 Treatment	IN CIRCULATORY ARREST 
 Start cardiopulmonary resuscitation (CPR) using standard protocols Manage arrhythmias using the same protocols, recognising that arrhythmias may be very refractory to treatment Consider the use of cardiopulmonary bypass if available GIVE INTRAVENOUS LIPID EMULSION (following the regimen overleaf) 
 Continue CPR throughout treatment with lipid emulsion Recovery from LA-induced cardiac arrest may take >1h Propofol is not a suitable substitute for lipid emulsion Lidocaine should not be used as an anti-arrhythmic therapy 	WITHOUT CIRCULATORY ARREST Use conventional therapist to treat: 
 hypotension, bradycardia, tachyarrhythmia CONSIDER INTRAVENOUS LIPID EMULSION (following the regimen overleaf) 
 Propofol is not suitable substitute for lipid emulsion Lidocaine should not be used as an anti-arrhythmic therapy
4 Follow-up	
 Arrange safe transfer to a clinical area with appropriate equipment and suitable staff until sustained recovery is achieved Exclude pancreatitis by regular clinical review, including daily amylase or lipase assays for two days Report cases as follows: 
 In the United Kingdom to the National Patient Safety Agency (via www.npsa.nhs.uk). In the Republic of Ireland to the Irish Medicines Board (via www.lmb.ie). If Lipid has been given, please also report its use to the International registry at www.lipidregistry.org. Details may also be posted at www.lipidrescue.org 	

Your nearest bag of Lipid Emulsion is kept

This guideline is not a standard of medical care. The ultimate judgement with regard to a particular clinical procedure or treatment plan must be made by the clinician in light of the clinical data presented and the diagnoses and treatment options available.

© The Association of Anaesthetists of Great Britain & Ireland 2009

Figure 1A. Reproduced by kind permission of the Association of Anaesthetists of Great Britain and Ireland and available for download at: www.aagbi.org/publications/guidelines/docs/la_toxicity_2010.pdf

[figure not shown]

Figure 1B. Reproduced by kind permission of the Association of Anaesthetists of Great Britain and Ireland and available for download at: www.aagbi.org/publications/guidelines/docs/la_toxicity_2010.pdf

DATA COLLECTION SHEET

Study Number: _____

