1. DEMOGRAPHIC DATA

Age	
Gender	Male/ Female
ASA	I/ II
Weight (kg)	
Height (m)	
Past medical illness (if any state current medications)	
Diagnosis	
Surgical Procedure	

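### Objective 1 compares end-tidal desflurane across ages 18 to 75 with an unadjusted t-test; age is already collected, and pre-specifying it as a covariate could gain precision at little cost

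*Combined protocol and SAP*

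**What the plan says.** - **Objective.** The first item under Objective is: "To investigate the effect of IV lignocaine on the end tidal desflurane concentration required to maintain BIS values between 40-60". The same measure is in the title. The plan does not use the word primary; I treat Objective 1 as the main comparison.
- **Population.** The Inclusion Criteria admit "Patients aged between 18-75 years of age", a span of 57 years.
- **Allocation.** Under Methodology, "Patients will be randomly assigned into two groups based on computer generated randomisation tables". No stratification, by age or anything else, is stated.
- **Measurement.** "BIS, MAC values, Et-Des concentration, BP and HR will be recorded every 10 min", from induction to the end of surgery. Each patient therefore has a series of Et-Des readings, and the plan does not say which value or summary is compared.
- **Age.** It is a field on the Data Collection Sheet, under "1. DEMOGRAPHIC DATA".
- **Analysis.** The Statistical Analysis section, part b), says: "Continuous variables will be compared using student's t -test", with "p value less than 0.05 will be regarded as statistically significant". It names no covariate.
- **Sample size.** Part a) uses a difference of 0.5, an SD of 0.4, alpha 0.01 and power 90%. This gives 21 per group, raised to 24 for dropout. It gives no unit for the 0.5 and 0.4 (I take them as vol% of Et-Des) and does not say what age range the SD reflects.

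**The concern.** If older patients need a different desflurane concentration from younger ones at the same BIS, age contributes to the between-patient spread of Et-Des. An unadjusted comparison leaves that part in the error term, so the interval is wider than the collected data require. In the realised trial, an arm that happens to be older also shifts the observed difference, and the planned analysis has no term to separate that shift from the effect of lignocaine.

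What is at stake is the precision of the Objective 1 estimate and how far a reader can rely on it if the baseline table shows an age gap. Adding age only after such a gap has been seen would be a data-driven choice, so the decision belongs in the plan.

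**Working it through.** **1. The plan's own figure.** A two-sided two-sample t-test with difference 0.5, SD 0.4, alpha 0.01 and power 90% (noncentral t) gives 88.5% power at 20 per group and 90.4% at 21. The stated 21 reproduces, and 10% dropout gives 24 per group and 48 in total. At the 0.05 threshold in part b), 21 per group gives 97.7%.

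**2. The unadjusted interval.** With 24 per arm and SD 0.4, the standard error of the difference is 0.4 × √(2/24) = 0.115. The 95% half-width is 2.013 × 0.115 = 0.232.

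**3. Effect of adjusting for age.** Let r be the within-arm correlation between age and the per-patient Et-Des value. The adjusted interval relative to the unadjusted one is approximately

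ratio = √[(1 − r²) × (46/45) × (1 + 1/44)].

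The first factor is the variance that age explains. The second is the residual degree of freedom lost (46 to 45). The third is the average variance inflation from chance age imbalance with 48 patients. The change in the t quantile (under 0.1%) is ignored.

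The documents give no value for r, so a range is shown. If 0.4 is the total SD, the age-driven part is r × 0.4 and cannot exceed 0.4.

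| r (assumed) | Age-driven SD, r × 0.4 | Ratio | Change in width | 95% half-width |
|---|---|---|---|---|
| 0 | 0 | 1.022 | +2% | 0.238 |
| 0.2 | 0.08 | 1.002 | 0% | 0.233 |
| 0.4 | 0.16 | 0.937 | −6% | 0.218 |
| 0.6 | 0.24 | 0.818 | −18% | 0.190 |

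The ratio equals 1 when (1 − r²) × 46/44 = 1, so r² = 2/46 and r = 0.21. Below that value adjustment costs up to about 2%; above it, adjustment gains.

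**4. What chance age imbalance does to the estimate.** The between-arm difference in mean age has standard error (age SD) × √(2/24). For an assumed age SD of 10 to 16.5 years (16.5 being uniform over 18 to 75), that is 2.9 to 4.8 years, with a 95% range of ±5.7 to ±9.3 years. The age SD cancels when the shift in the Et-Des difference is expressed through r:

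95% range of the shift = ±1.96 × r × 0.4 × √(2/24) = ±0.226 × r.

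This is ±0.05 at r = 0.2, ±0.09 at r = 0.4 and ±0.14 at r = 0.6, or 9%, 18% and 27% of the planned 0.5. These shifts are part of the 0.232 half-width in step 2, not an addition to it. Adjustment removes the part that is linear in age.

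**5. Validity of the t-test.** In 40,000 simulated trials per setting, with 21 per group, no drug effect, ages uniform over 18 to 75 and outcome falling by 0.02 or 0.04 per year of age, the unadjusted t-test rejected in 4.9% and 5.0% of trials at 0.05, and in 1.0% and 1.1% at 0.01. Type I error is nominal.

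**The case against.** **The premise is outside the documents.** They do not say that desflurane requirement varies with age, and they give no slope, age SD or mean Et-Des. Elderly patients appear in the Introduction only in connection with faster offset. This stands. The age effect is therefore an assumption, and the gain is given only as a range that starts at a small loss.

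**The planned test is already valid.** This also stands. A reader might infer that an age imbalance would be mistaken for a drug effect, in the sense of too many false positives. The documents do not support that: allocation is randomised, and the simulation shows nominal error rates. Imbalance affects the point estimate of a given trial, and the reported standard error allows for it.

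**No power shortfall is shown.** A reader might also infer that age spread leaves the trial underpowered. On the plan's own inputs power is 90.4% at alpha 0.01. Lower figures arise only if the SD of 0.4 excludes age spread, which the plan does not say. On that reading, with an assumed slope of 0.01 to 0.03 vol% per year and age SD of 10 to 16.5 years, unadjusted power with 21 per group would be 88% down to 45% at 0.01 (97% to 70% at 0.05). The low end needs the steepest slope and a uniform age distribution together. These figures show sensitivity to the assumptions; they are not a finding about this trial.

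**MAC is recorded too.** The general t-test sentence would cover it as a continuous variable. But the plan names no specific role for MAC and does not say whether the readings are corrected for age, so they cannot be counted as an allowance for age.

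**Conclusion.** The point holds as a matter of precision. The plan makes no allowance for age in allocation or in the Objective 1 analysis, although age is collected. Adjustment would change the interval width by about +2% (r = 0), 0% (r = 0.2), −6% (r = 0.4) or −18% (r = 0.6). It would also remove from the estimate a chance shift whose 95% range is ±0.05 to ±0.14 for r between 0.2 and 0.6.

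These figures assume 24 analysed per arm, a total SD of 0.4 in vol%, and a linear age relation that is the same in both arms. Whether r is near 0 or near 0.6 cannot be settled from the documents. The stronger readings (a biased comparison, an inflated false-positive rate or an underpowered trial) are not supported. The change is worth making because its possible gain is several times its cost.

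**What to change.** Before unblinding, amend part b) of the Statistical Analysis section so that Objective 1 is analysed as follows:

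- Define one Et-Des value per patient, for example the mean of that patient's maintenance readings, and state which time points count.
- Fit a linear model of that value on group and age in years (continuous).
- Report the age-adjusted between-group difference with its 95% confidence interval as the main result for Objective 1.
- Keep the unadjusted t-test as a supporting result.

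The cost is a short amendment and one degree of freedom. If age is unrelated to Et-Des, the interval is about 2% wider on average (half-width 0.238 instead of 0.232). No new data, extra patients or change to patient care is needed. The per-patient Et-Des value has to be defined in any case, because the t-test cannot be run on a series of 10-minute readings without it.

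### Procedures of mixed urgency are pooled with no stratification named and an unadjusted t-test; adjusting for elective/emergency class is a cheap way to recover any precision lost

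*Combined protocol and SAP*

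**What the plan says.** Inclusion Criteria items 3 to 6 admit four laparoscopic procedures:

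- "Patients scheduled for elective laparoscopic cholecystectomy"
- "Patients scheduled for laparoscopic hernioplasty"
- "Patients scheduled for emergency laparoscopic appendicectomy"
- "Patients scheduled for emergency laparoscopic cystectomy"

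One is labelled elective and two emergency; hernioplasty carries no label.

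On allocation, the Methodology section says: "Patients will be randomly assigned into two groups based on computer generated randomisation tables". It names no strata, blocks or minimisation. The Statistical test section says: "Continuous variables will be compared using student's t -test". It names no covariate or stratum term. The data collection sheet has a field for "Surgical Procedure" under demographic data.

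The Introduction remarks of lignocaine infusion that "its clinical effectiveness differs between types of surgery, possibly due to sample size and design of the studies".

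**The concern.** Patients are recruited at the premedication round for a scheduled operation, so the procedure and its urgency are known before allocation. The plan records the procedure but uses it in neither the allocation nor the analysis.

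If elective and emergency patients need different Et-Des to hold the BIS target, or have different BP and HR, that difference goes into the error term of the t-test. The confidence interval is then wider than it need be and power is lower. With 24 patients per arm, a visible imbalance in emergency share is also quite possible, and the plan has no prespecified adjusted estimate to turn to if one appears.

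**Working it through.** **1. The plan's own figure.** Inputs from the sample size section: δ = 0.5, σ = 0.4, alpha 0.01, power 0.9, 1:1. With n = 21 per group the noncentrality is 0.5 / (0.4 × √(2/21)) = 0.5 / 0.1234 = 4.05. The two-sided critical value on 40 df is 2.704, and the noncentral t gives power 90.4%. So 21 per group reproduces. For 10% dropout, 21/0.9 = 23.3, rounded up to 24 per group and 48 in all. At the 0.05 threshold stated for the analysis, the same 21 per group has power 97.7%.

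**2. Class difference added to the noise.** The documents give no class difference D and no case mix. Assume half the cases are emergencies and 0.4 is the SD within a class. Then total SD = √(0.4² + 0.5 × 0.5 × D²) = √(0.16 + D²/4). Power of the unadjusted t-test for δ = 0.5, 21 per group:

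| D (vol%) | Total SD | SD relative to 0.4 | Power, alpha 0.01 | Power, alpha 0.05 |
|---|---|---|---|---|
| 0 | 0.400 | 1.00 | 90.4% | 97.7% |
| 0.2 | 0.412 | 1.03 | 88.3% | 97.0% |
| 0.4 | 0.447 | 1.12 | 81.5% | 94.2% |
| 0.6 | 0.500 | 1.25 | 70.2% | 88.5% |

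**3. The other reading of σ.** If 0.4 already includes the case mix, unadjusted power stays at 90.4%. The within-class SD would then be √(0.16 − D²/4), that is 0.387, 0.346 or 0.265 for the three values of D, and adjustment would raise power above the stated figure. The sample size section does not say which reading applies.

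**4. What adjustment recovers.** By simulation at D = 0.4 and 0.6 (0.4 within class, 21 per group, alpha 0.01), a linear model with arm and class has power of about 89.5%. Allocation in blocks of four within class plus the same model gives about 90%. In a simulation with 24 per group and unstratified allocation, the adjusted 95% confidence interval is about 1% wider than the unadjusted one if D = 0, and about 2%, 10% and 19% narrower at D = 0.2, 0.4 and 0.6.

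**5. Chance imbalance.** Treat the emergency counts in two arms of 24 as independent binomials. The arms differ by 5 or more emergency patients with probability 19% if half are emergencies, and 16% if 30% are. A difference of 5 patients moves the Et-Des contrast by (5/24) × D = 0.042, 0.083 or 0.125 vol% for the three values of D. The standard error at 24 per arm, total SD × √(2/24), is 0.119, 0.129 or 0.144, so each shift is within one standard error. The variance behind these shifts is already in the total SD of step 2.

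**6. Validity.** Simulated type I error of the unadjusted t-test at the 0.05 level is 5.1% at D = 0.4 and 4.9% at D = 0.6.

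**The case against.** Much of the case on the other side stands.

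- **Validity.** An unstratified, unadjusted comparison is a sound design for a single-centre trial of 48 patients.
- **Limited heterogeneity.** All procedures are laparoscopic, in ASA I or II patients of 50 to 100 kg, lasting one to three hours, with a common induction regimen, gas mixture and BIS target.
- **Undocumented D.** Values of 0.4 and 0.6 are 80% and 120% of the whole planned drug effect, and nothing in the documents supports them. At 0.2 the loss is about two points of power at alpha 0.01.
- **Threshold.** At the 0.05 level that the analysis applies, power stays near or above the 90% target in every row of the table.

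Three stronger readings are tempting, and the documents do not support them.

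- A reader might infer that the plan contradicts its own rationale, since it reports that effectiveness varies with surgery and then pools. The Introduction's sentence carries its own qualifier, that sample size and study design may explain the variation. It concerns clinical effectiveness in general, not Et-Des. It also describes a drug effect that varies with surgery (an interaction), whereas the precision loss needs the procedure itself to shift Et-Des, which the documents nowhere state.
- A reader might infer that chance imbalance biases the trial. Randomisation keeps the estimate unbiased on average and type I error is held. The imbalance shift is the same precision loss seen in one sample, not a second harm.
- A reader might count two elective and two emergency procedures. Hernioplasty is not labelled, so that count is an inference.

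What survives is narrower. A factor known before allocation and already recorded goes unused, and nothing shows that σ = 0.4 represents this mix. By their titles, the two studies cited for the calculation concern colonic surgery in one case and sevoflurane requirements in the other.

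**Conclusion.** The point holds as a cheap, optional improvement. The planned analysis is valid; what it may give up is precision. The size runs from nil to material, depending on a class difference that the documents do not give: nil if the classes do not differ, or, measured against the stated power, if σ = 0.4 already covers the mix. If 0.4 is a within-class SD and half the cases are emergencies, a class difference of 0.6 vol% takes about 20 points off power at alpha 0.01 (90.4 − 70.2) and about 9 at 0.05 (97.7 − 88.5). No stratification is specified; the text does not rule out that the tables will be stratified, so the sponsor may only need to say so. The figures are for Et-Des. The documents give no SD for BP or HR, so the same argument applies to them without a number.

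**What to change.** In the Statistical test section, replace the unadjusted t-test for the Et-Des, BP and HR comparisons by a linear model with treatment arm and elective/emergency class. Define the classes in advance, including the one to which hernioplasty belongs. State whether σ = 0.4 is meant to cover the mixed population. If randomisation has not begun, also generate the allocation in permuted blocks within the two classes. If it has, the model alone recovers nearly all of the benefit. Prespecifying the factor also avoids choosing an adjustment after an imbalance has been seen.

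The cost is a sentence or two in the SAP, one model degree of freedom (a confidence interval about 1% wider if the classes do not differ) and a second list for the registrar who prepares the syringes. Two classes still pool procedures within each class, and a main-effect factor does not address a drug effect that differs between surgeries.
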